#### **10.4.4.4 Additional Subgroup Analysis**

In order to provide additional characterization and interpretation of the primary effectiveness and safety outcomes, subgroup analyses based on various prognostic factors may be performed in the PP population for the primary effectiveness endpoint and in the SP for the primary safety endpoint.

### **10.4.5 Exploratory Analyses**

#### **10.4.5.1 Logistic Regression Analyses**

Univariate and multivariate logistic regression analyses will be performed to examine the impact of demographic and baseline characteristics (e.g., age, gender, ethnicity, LA size, AF duration, medical history, etc.) on the primary outcomes. The outcome variables (i.e., primary effectiveness and safety outcomes) will be the dependent variables and baseline and demographic characteristics will be treated as independent variables. Univariate logistic regression models will be conducted for each of the potential predictors. A p-value <0.20 will be the cut-off point for screening covariates. Model selection methods (e.g., forward selection, etc.) will be applied in the multivariate model to identify the best set of predictors for the outcomes. The identification of relevant predictors provides additional characterization and interpretation of

the primary effectiveness and safety outcomes. These analyses will be performed in the PP population for the primary effectiveness endpoint and in the SP for the primary safety endpoint.

#### **10.4.5.2 Time to Event Analysis**

Kaplan-Meier curves and survival estimates will be provided for AF/AT/AFL recurrence. This analysis will include all subjects in the PP and mITT and account for censored observations. The survival probabilities of AF/AT/AFL recurrence at 15 months follow-up along with the corresponding 95% confidence intervals using Greenwood's formula will also be presented.

### **10.5 Analyses of Secondary Endpoints**

Descriptive statistics and two-sided 95% confidence intervals using the exact method will be presented for the secondary effectiveness and safety endpoints. No formal statistical hypothesis and inferential statistics will be formulated and performed for the secondary effectiveness and safety endpoints. Analyses of all secondary endpoints will be performed in the proposed analysis populations excluding the subjects with missing outcomes.

#### **10.5.1 Secondary Effectiveness Endpoints**

##### **10.5.1.1 Acute Procedural Success**

The number and percentage of subjects with acute procedural success and the corresponding 95% exact binomial confidence interval will be presented. Analysis will be conducted based on PP population.

##### **10.5.1.2 15-Month Single Procedure Success**

The following analyses will be performed in the PP population:

- The 15-month single procedure success will be presented treating the endpoint as a binary variable. The point estimate and the corresponding two-sided 95% confidence interval will be presented.
- Kaplan-Meier analysis: this analysis will include all subjects in the PP population. Subjects with less than 15-month follow-up will be censored at their last observations.

#### **10.5.2 Secondary Safety Endpoints**

##### **10.5.2.1 Occurrence of Serious Adverse Events (SAEs)**

Serious AEs will be reported by three timeframes (ablation to  $\leq 7$  days,  $>7$  to 30 days, and  $>30$  days post ablation).

- Occurrence of Early Onset (within 7 days of initial ablation) SAE
- Occurrence of Peri-Procedural (>7 to 30 days) SAE
- Occurrence of Late Onset (>30 days) SAE

The percentage of subjects experiencing the occurrence of serious AEs within each timeframe after the initial ablation procedure and the corresponding 95% exact binomial confidence interval will be presented. Serious AEs in different timeframes will be further evaluated by causality and severity using descriptive statistics. Analysis will be conducted based on safety population.

## **10.6 Analyses of Additional Endpoints**

### **10.6.1 15-Month Effectiveness Success – Post Medication Adjustment Period (Day 91-450)**

The following analyses will be performed for both documented all-cause AF/AFL/AT recurrence and documented symptomatic AF/AFL/AT recurrence in the PP population:

- The 15-month effectiveness success rate post 3-Month Medication Adjustment Period will be presented for subjects in the PP population treating the endpoint as a binary variable. The point estimate and the two-sided 95% confidence interval will be presented.
- Kaplan-Meier analysis: this analysis will include all subjects in the PP population. Subjects with less than 15-month follow-up will be censored at their last observations.

### **10.6.2 15-Month Effectiveness Success – Post Therapy Consolidation Period (Day 181-450)**

The following analyses will be performed for both for both documented all-cause AF/AFL/AT recurrence and documented symptomatic AF/AFL/AT recurrence in the PP population:

- The 15-month effectiveness success rate post 3-Month Therapy Consolidation Period will be presented for subjects in the PP population treating the endpoint as a binary variable. The point estimate and the two-sided 95% confidence interval will be presented.
- Kaplan-Meier analysis: this analysis will include all subjects in the PP population and subjects with less than 15-month follow-up will be censored at their last observations.

### **10.6.3 Procedural Data**

Procedural data such as procedure duration, fluoroscopy duration, power, fluid delivery, output and balance will be summarized with descriptive statistics. These analyses will be conducted using the PP population.

- % PVI isolation with the study device(s) by PV

- Repeat Ablation Rate
- Total Fluoroscopy Time
- Overall Procedure Time
- Duration of RF application time
- RF Ablation parameters per application
- Device(s) utilized (per ablation)
- Duration of mapping time
- VISITAG Settings
- CF range
- Power range

#### **10.6.4 Ablation Index Assessment per Anatomical Region**

Ablation index data (force, power, and time) will be collected in the CARTO® 3 system during the procedures. The data will be processed to generate the ablation index and the ablation index will be characterized in the PP population and safety population. Characterization of ablation index may include:

- Descriptive statistics: average, median, min, max, 1st and 3rd quartiles
- Correlation to acute effectiveness and primary effectiveness and safety outcomes where appropriate

#### **10.6.5 Quality of Life**

Quality of Life (QOL) status will be evaluated by assessing AFEQT and arrhythmia-specific Symptom Frequency and Severity Checklist outcomes. Descriptive statistics for QOL measurements will be reported. These analyses will be conducted using the PP population.

##### **10.6.5.1 AF Effect on Quality of Life**

The AF Effect on QualiTy of life survey (AFEQT) is a questionnaire used to assess the quality of life, specifically for atrial fibrillation patients. AFEQT assess quality of life from three domains, including symptoms, daily activities, and treatment concerns with 18 questions on a seven-point Likert scale. Two additional questions are designed to assess the treatment satisfaction, which will not be included in the overall AFEQT score calculation .

The overall AFEQT score and subscales scores for symptoms, daily activities, and treatment concern will be calculated based on the guideline – “Atrial Fibrillation Effect on QualiTy-of-life

(AFEQT) Questionnaire Instruction and Scoring Manual, version 1.0)". Descriptive statistics for the baseline and changes-from-baseline measurements of overall AFEQT score and subscale scores will be presented by follow-up visits.

#### **10.6.5.2 AF Symptom Frequency and Severity Checklist**

The symptom frequency score (SFS) and symptom severity score (SSS) will be calculated based on the guideline provided by Buben, R.S. & Kay, G.N., and revised by Jenkins, L.S., 1993. Descriptive statistics for the baseline and changes-from-baseline measurements of SFS and SSS will be presented by follow-up visits.

#### **10.6.6 Ablation Strategies Post-PVI**

Ablation strategies post PVI will be recorded during the AF ablation procedure. Combinations of ablation strategies post PVI will be characterized in the PP population. Characterization of ablation strategies post PVI may include:

- Descriptive statistics: number and percentage of subjects in different ablation strategy
- Acute effectiveness, primary effectiveness and safety outcomes by ablation strategies

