### 8 Analysis Sets

For the analysis of study endpoints, the analysis populations are defined as the following:

- **Modified Intent-To-Treat (mITT) Population:** the mITT population will consist of all enrolled subjects who meet all eligibility criteria AND in whom
  - (1) RF energy was delivered with study catheter OR
  - (2) Study catheter was inserted but no RF energy was delivered
- **Safety Population (SP):** The safety population will consist of all enrolled subjects who have undergone insertion of the study catheter. Safety endpoints will be analyzed based on the Safety Population.
- **Per Protocol (PP) Population:** The PP population will include subjects who satisfy the following criteria:
  - are enrolled and meet all eligibility criteria
  - have undergone RF ablation
  - are treated with the study catheters, and have been treated for the study-related arrhythmia

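### SAP 10.6.6 names only the per-protocol population for safety outcomes by post-PVI strategy, while SAP 8 assigns safety endpoints to the Safety Population (minor; one descriptive table)

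*SAP*

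**What the plan says.** SAP 10.6.6 covers the ablation strategies used after pulmonary vein isolation. It names a single population: "Combinations of ablation strategies post PVI will be characterized in the PP population". It continues with "Characterization of ablation strategies post PVI may include", and one of the two items listed is "Acute effectiveness, primary effectiveness and safety outcomes by ablation strategies".

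SAP 8 sets the general rule for safety: "Safety endpoints will be analyzed based on the Safety Population". It defines that set broadly: "The safety population will consist of all enrolled subjects who have undergone insertion of the study catheter". The PP population is narrower. Its members must meet three conditions: they "are enrolled and meet all eligibility criteria", they "have undergone RF ablation", and they "are treated with the study catheters, and have been treated for the study-related arrhythmia".

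Protocol 4.3 and SAP 6.3 both commit to characterising the safety and the effectiveness of the post-PVI strategies. Neither names a population for it.

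**The concern.** The Safety Population has no eligibility condition and PP has one. A subject who was ablated and later found to have broken an entry criterion is therefore in the Safety Population and outside PP. If that subject had a tamponade or a stroke, the event would count in the primary safety analysis but appear in no row of the by-strategy safety table.

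The loss is unlikely to be neutral. Protocol 1.3.2 says the exclusion criteria were drawn up to keep out people whose history or condition raises their risk of adverse events. On that reasoning, the ablated subjects who fall outside PP on eligibility would tend to have the higher event rate, and the by-strategy rates would tend to be too low.

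What is at stake is the accuracy of one descriptive safety table, and whether a reader can trace its events to the primary safety result.

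**Working it through.** The plan states no figure on this point, so there is none to reproduce. The check compares the sections and then illustrates the size.

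**Step 1. Which population the SAP names for safety outcomes**

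| SAP section | Content | Population named for safety |
|---|---|---|
| 8 | General rule | Safety Population |
| 10.4.2 | Primary safety endpoint | Safety Population |
| 10.4.3.2 | Missing-data sensitivity, safety | Safety Population |
| 10.4.4.1, 10.4.4.2 | Site and region heterogeneity | None named |
| 10.4.4.3, 10.4.4.4 | Sex and other subgroups | Safety Population (PP for effectiveness) |
| 10.4.5.1 | Logistic regression | Safety Population (PP for effectiveness) |
| 10.5.2.1 | Serious adverse events | Safety Population |
| 10.6.4 | Ablation index, including correlation with safety | PP and Safety Population |
| 10.6.6 | Post-PVI strategies, including safety | PP only |

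Wherever else the SAP names a population for safety outcomes, the Safety Population is included. Section 10.6.6 is the one exception, and it gives no reason.

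**Step 2. Who is lost**

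- Catheter inserted, no RF delivered: in the Safety Population, not in PP. These subjects have no post-PVI strategy, so their absence from a by-strategy row is no loss.
- Ablated, failed an eligibility criterion: in the Safety Population, not in PP. Lost from the table.
- Ablated, but not treated as the third PP condition requires: in the Safety Population, not in PP. Lost from the table.

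**Step 3. Illustrative size**

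The documents give neither the number of ablated subjects outside PP nor their event risk. The assumptions are:

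- a strategy group of n = 50 with 4 events, so 4/50 = 8.0%, which matches the anticipated primary safety rate in SAP 9.2;
- k = 2 to 4 of the 50 outside PP;
- event risk q among those k of 8% (the anticipated rate) to 16% (twice that).

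Expected PP rate = (4 − k·q) / (50 − k):

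| k | q | Calculation | Expected PP rate |
|---|---|---|---|
| 2 | 8% | (4 − 0.16)/48 | 8.0% |
| 4 | 8% | (4 − 0.32)/46 | 8.0% |
| 2 | 16% | (4 − 0.32)/48 | 7.7% |
| 4 | 16% | (4 − 0.64)/46 | 7.3% |

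The expected rate therefore reads 7.3% to 8.0% instead of 8.0%. With k = 0 there is no effect.

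**The case against.** The case for leaving the text alone has four parts.

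1. *There may be no conflict.* The SAP lists safety endpoints under its primary and secondary headings, and the strategies are an additional endpoint. Alternatively, the SAP 8 sentence may already govern the safety item in 10.6.6. Either reading is possible. But 10.6.6 names PP without qualification, and a programmer would follow the specific sentence. Section 10.6.4, also an additional endpoint, names the safety population explicitly. The ambiguity needs settling on either reading.
2. *The table is optional in form.* The wording is "Characterization of ablation strategies post PVI may include". This stands as a limit: the SAP permits the safety tabulation here and does not fix it. Protocol 4.3 and SAP 6.3 nevertheless say safety will be characterised, and PP is the only population offered for doing so.
3. *No conclusion depends on it.* This stands in full. SAP 7 tests only the primary endpoints, Protocol 7.7 makes additional endpoints descriptive, and SAP 10.4.2 and 10.5.2.1 keep the primary safety and serious adverse event analyses in the Safety Population.
4. *Few subjects should be affected.* Protocol 3.0 sends to ablation only enrolled subjects who satisfy all eligibility criteria. This stands too, and the number may be zero.

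Two stronger readings are tempting, and the documents support neither.

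- A reader might infer that more extensive ablation would be made to look safer than it was. Eligibility applies to every strategy, and no section suggests that ineligible subjects cluster in the linear-lesion or CFAE groups.
- A reader might work an example in which one whole event drops out with 2 to 4 subjects, so that 4/50 = 8.0% becomes 3/48 = 6.3% or 3/46 = 6.5%. That can happen by chance. It implies an event risk of 1/4 to 1/2 (25% to 50%) among those removed, well above the 8% to 16% assumed here, so it is not the expected effect.

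**Conclusion.** The point holds as a minor inconsistency. SAP 10.6.6 names a population for safety outcomes that departs from SAP 8 and from every other section that names one. Followed literally, it drops events in ablated subjects outside PP. Protocol 1.3.2 supports a downward direction, as a tendency only.

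The size is unknown and may be nil. Under the assumed 2 to 4 of 50 subjects outside PP with a risk of 8% to 16%, the expected reading is about 7.3% to 8.0% against 8.0%. Those inputs are assumptions and have no source in the documents. The primary safety test and the serious adverse event summaries are unaffected, and every event missing from this table is still counted in the Safety Population analyses. Lowest severity.

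**What to change.** In SAP 10.6.6, replace the single population with a split: safety outcomes by strategy in Safety Population subjects who received RF, and acute and primary effectiveness by strategy in PP. This is the division that 10.4.4.3, 10.4.4.4 and 10.4.5.1 already use.

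Restricting to subjects who received RF still omits those with the catheter inserted and no RF, who do count in the primary safety analysis. List events in those subjects on a separate line, so that the table total reconciles with the primary safety result.

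The cost is one or two sentences in the SAP and one extra table line. It needs no new data and changes no primary or secondary analysis.

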#### **10.7 Health Economic Data**

The health economic data collected in this study includes the cost and frequency of health care utilization during hospitalization for the study index ablation procedure, as well as any additional hospitalizations during the study period. Because this data does not support the safety and effectiveness of the study catheters and the EPU, it will not be presented in the final report.

